**Table 2. Patient Demographic and Clinical Characteristic Variables at Index**

Variable	Operational definition
Age	Age will be defined as of the index date and will be used to assign patients to age groups: 18-29, 30-49, 50-64, 65-74, $\geq 75$ years and unknown/missing age.
Gender	Defined as of the index date as the distribution of female, male and unknown/missing sex patients.
Region	Kingdom of Bahrain
Nationality	Nationality of the patient will be mentioned
Enrollment Date Place of Service (POS)	Distribution of patients by the type of outpatient encounter during the enrollment date (eg, office visit, emergency room (ER), outpatient hospital, other, etc.).
Enrollment Date	Date (defined as MM/YYYY) of the enrollment date specified for each Cohort.

Variable	Operational definition
Specialty of Provider at enrollment Date	Distribution of the provider specialties present during the enrollment date. Patients with no provider specialty recorded will be included in an “Unknown/missing specialty” category.
Patient-reported COVID-19 symptoms	
List of COVID-19 symptoms to be added by study team (US, CDC definition).
 
1- Stuffy or runny nose 2- Sore throat 3- Shortness of breath 4- Cough 5- Low energy/tiredness/fatigue 6- Muscle ache/body aches 7- Headache 8- Chills or shivering 9- Feeling hot/feverish 10- Nausea or vomiting 11- Diarrhea 12- Loss of sense of smell 13- Loss of sense of taste

COVID-19 Symptom Onset Date	Date of symptom onset during the post-Paxlovid™ availability timeframe.
Time to COVID-19 Symptom Resolution	The number of continuous days with the same COVID-19 symptom. When available, the number of consecutive days will be reported as counts and percentages. The date of symptom resolution (last date recorded) will be reported when available.
Date of COVID-19 Vaccination	Date of each COVID-19 vaccination received. Note: patient-specific vaccination history may require more than 6-months pre-index time period.
Date of Paxlovid™ prescription written and/or fill history (eg, prescription claim)	Date of Paxlovid™ prescription written or fill history. Note: if both dates are available within the database, use the most recent date provided.

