### **Data source**

This study will involve a secondary data analysis of COVID-19 patients' data from the ISeha Electronic health records. The following data will be used: patient demographic characteristics, clinical characteristics, and COVID-19 disease outcomes. The ISeha EHR data will be anonymized. Demographic and clinical data from eligible patients were recorded in ISeha electronic health records by medics on the ward. Patient-reported symptom outcomes in the five-days following Paxlovid prescription were determined by a follow-up telephone call.

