**Table 1: Patient Demographic Variables**

Variable	Operational definition
Group	Received Paxlovid or did not receive Paxlovid
Age	Age will be defined as of the date of COVID-19 diagnosis using a PCR test and will be used to assign patients to age groups: 18-29, 30-49, 50-64, 65-74, $\geq 75$ years and unknown/missing age
Sex	Female, male and unknown/missing sex patients
Nationality	Nationality of the patient (Bahrain, other Middle East and North Africa, India, Pakistan, South East Asia, Caucasian)
Enrollment Date Place of Service (POS)	Type of outpatient encounter during the enrollment date (e.g., office visit, emergency room (ER), outpatient hospital, other, etc.)
Enrollment Date	Date (defined as MM/YYYY) of the enrollment date specified
Specialty of Provider at enrollment Date	Provider specialties present during the enrollment date. Patients with no provider specialty recorded will be included in an “Unknown/missing specialty” category
COVID-19 Symptom Onset Date	Date of symptom onset prior to presentation to healthcare facility

PFIZER CONFIDENTIAL

CT24-WI-GL03-RF03 2.0 *Non-Interventional Statistical Analysis Plan For Secondary Data Collection*  
*Study 01-Jun-2020*  
 Page 8 of 22

Time to COVID-19 Symptom Resolution	Time from onset of COVID-19 symptoms to resolution of symptoms
Date of COVID-19 Vaccination	Date of each COVID-19 vaccination received. Note: patient-specific vaccination history may require more than 6-months pre-index time period.
Date of Paxlovid prescription written and/or fill history (e.g., prescription claim)	Date of Paxlovid prescription written or fill history. Note: if both dates are available within the database, use the most recent date provided.

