### Inferential statistics

Between-group differences in categorical variables will be examined using proportions tests, Chi-square tests of independence or Fisher exact tests as appropriate. Differences in continuous variables will be examined using independent t-tests.

Differences in proportions or means (as appropriate) and 95% confidence intervals between COVID-19 patients taking Paxlovid, and COVID-19 patients who were offered Paxlovid therapy but who refused treatment will be reported. Additionally, Cramer's V or Cohen's d will be reported.

Cramer's V is a measure of association that quantifies the strength and direction of the relationship between the two categorical variables being compared. Cramer's V ranges from 0 to 1, where 0 indicates no association between the variables, and 1 represents a perfect association. The magnitude of Cramer's V will be interpreted as follows:

Cramer's V	Effect Size
-------------------	--------------------

0.1	Weak
0.3	Medium
0.6	Large

Cohen's d quantifies the standardized difference between the means of the two groups, and is calculated by taking the difference between the means of the two groups and dividing it by the pooled standard deviation. The magnitude of Cohen's d will be interpreted as follows:

Cohen's d	Effect Size
------------------	--------------------

0.2	Small
0.5	Medium
0.8	Large

An a priori alpha level of 0.05 has been selected for all tests. As this work is exploratory no adjustment for multiple comparisons will be made.

PFIZER CONFIDENTIAL

CT24-WI-GL03-RF03 2.0 *Non-Interventional Statistical Analysis Plan For Secondary Data Collection*  
Study 01-Jun-2020  
Page 14 of 22

Selection of the control groups will consider the following characteristics based on the availability of data using propensity-score matched:

- age,
- sex,
- COVID vaccination status,
- high-risk status for severe COVID-19 outcomes (WHO definition),
- assessment of healthcare seeking behavior in 365 days prior to COVID infection (such as flu or streptococcus pneumoniae vaccine, has primary healthcare provider, number of primary care/hospital visits),
- socioeconomic factors (such as household income, employment status),
- geographic location of residence,
- comorbidities.

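### Two of the eight propensity-score factors (socioeconomic factors and residence) have no extracted variable, and a third (healthcare seeking) is only partly covered; nationality is collected but not in the score

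*SAP*

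**What the plan says.** SAP 1.13 (Inferential statistics) introduces the list with "Selection of the control groups will consider the following characteristics based on the availability of data using propensity-score matched". The eight factors are age, sex, COVID vaccination status, WHO high-risk status, healthcare seeking, socioeconomic factors, residence and comorbidities. Three matter here:

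- Healthcare seeking: "assessment of healthcare seeking behavior in 365 days prior to COVID infection", with influenza or pneumococcal vaccination and "has primary healthcare provider, number of primary care/hospital visits" as examples.
- Socioeconomic position: "socioeconomic factors (such as household income, employment status").
- Residence: "geographic location of residence".

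On what is extracted, the SAP's Data source section states: "The following data will be used: patient demographic characteristics, clinical characteristics, and COVID-19 disease outcomes". SAP Table 1 includes "Nationality of the patient (Bahrain, other Middle East and North Africa, India, Pakistan, South East Asia, Caucasian"). The location row in Protocol Table 2 reads "Region Kingdom of Bahrain". SAP 1.11 (Covariates) is marked not applicable. Protocol 9.7 describes no matching, so neither section defines inputs for the score.

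**The concern.** The contrast is between patients who accepted an offered drug and patients who refused it. SAP 1.12 and its table shells attach p-values and effect sizes to hospitalization, ICU admission and death. Willingness to seek care, access to care and social position could plausibly affect both acceptance and later admission. The SAP's own list shows that its authors think so too.

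Protocol 9.4.1 and 9.6 say that I-Seha records are unstructured and that staff abstract them into an eCRF. A field that is not on the extraction list will therefore be unavailable at analysis, whether or not I-Seha holds it. The availability condition then removes the factor without comment. The SAP does not say which factors may drop out, what replaces them or how the gap is reported. A reader of the results could credit the study with an adjustment that was never made.

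**Working it through.** The plan gives no figure to reproduce. The main check sets each matching factor against the variable tables (Protocol Tables 2 to 6 and 8; SAP Tables 1, 2 and 4).

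| Factor | Listed variable | Status |
|---|---|---|
| Age | SAP Table 1 | available |
| Sex | SAP Table 1 | available |
| COVID vaccination status | derivable from vaccination dates, SAP Table 1 | available |
| WHO high-risk status | derivable from SAP Table 2 and the WHO groups listed after SAP Table 4 | available |
| Comorbidities | SAP Table 2; Protocol Tables 3 and 6 | available |
| Healthcare seeking | baseline all-cause hospitalizations and length of stay, SAP Table 4 and Protocol Table 4 | partial |
| Socioeconomic factors | none | absent |
| Residence | Protocol Table 2 region, a single value; no region row in SAP Table 1 | absent |

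Count: 5 available + 1 partial + 2 absent = 8.

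**Healthcare seeking.** Protocol 9.3 sets the baseline period at one year before index, close to the SAP's 365-day look-back, so baseline admissions cover the hospital part of the visit count. They do not cover preventive vaccination, having a primary provider or primary-care visits, and admissions reflect severity of illness as well as care seeking. Other fields come near without filling the gap. Place of service and provider specialty describe the enrollment encounter only. Time to first outpatient encounter is counted from the COVID diagnosis. Protocol Table 8 names outpatient and emergency room visits, but as outcomes with no baseline definition.

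**Region.** A variable with one level has zero variance. It adds nothing to a propensity model and gives no balance to check.

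**Nationality.** Six categories are collected and compared between groups in the SAP's baseline shell (Table 3); none enters the score.

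**Illustrative size.** Suppose an unmeasured binary trait has prevalence p1 in acceptors and p0 in refusers, and multiplies admission risk by r. If the drug has no effect and the matching leaves the trait untouched, the expected risk ratio is

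(1 + p1(r − 1)) / (1 + p0(r − 1)).

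All inputs are assumptions; the documents give none.

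- p1 = 0.6, p0 = 0.4, r = 0.67: 0.802 / 0.868 = 0.92
- p1 = 0.6, p0 = 0.4, r = 0.5: 0.70 / 0.80 = 0.875
- p1 = 0.7, p0 = 0.3, r = 0.67: 0.769 / 0.901 = 0.85
- p1 = 0.7, p0 = 0.3, r = 0.5: 0.65 / 0.85 = 0.76

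If the trait is instead commoner in refusers (p1 and p0 exchanged), each result becomes its reciprocal:

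- 0.868 / 0.802 = 1.08
- 0.80 / 0.70 = 1.14
- 0.901 / 0.769 = 1.17
- 0.85 / 0.65 = 1.31

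The direction also reverses if the trait is commoner in acceptors but raises the chance of admission, for example because frequent users of care are admitted more readily.

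**The case against.** The strongest reply is that the plan is conditional and modest. The matching list depends on availability, the SAP states no hypotheses and calls the work exploratory, the protocol's primary objective is descriptive, and Protocol 9.9 says that only association can be shown. Nationality is reported by group with a p-value and effect size, so an imbalance would be visible. Nothing in the documents says that nationality stands in for social position or access to care. Abstraction is manual, with all 8263 records to be reviewed, so new fields are not free.

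Part of this stands. Treating nationality as a proxy is a judgment, and extra fields do cost effort. But the availability condition does not cure the gap, because the extraction list itself determines what is available. The exploratory label does not remove the planned tests on outcomes, and 9.9 names no unmeasured confounder.

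A reader might also infer more than the documents support:

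- That three factors have no variable at all. Baseline-year hospitalizations are extracted and partly cover healthcare seeking.
- That matching cannot balance the missing factors. Matching on age, vaccination, comorbidities, WHO risk status and, if used, prior admissions may balance correlated traits incidentally. What is lost is direct control and any check of balance.
- That the comparison is biased in the drug's favour. The documents establish neither direction nor size.

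**Conclusion.** The point holds as a mismatch between the matching list and the extraction list. Two of eight factors have no variable, a third is only partly covered, and a collected baseline variable is left out of the score. The acceptor-versus-refuser comparison of outcomes may therefore keep confounding of unknown direction. The spurious risk ratios of 0.76 to 0.92, or 1.08 to 1.31, show only what moderate imbalance could do. They rest on assumed prevalences and trait effects and on no incidental balance from the other factors. The count of factors rests on the variable tables alone and needs no assumption. Whether I-Seha holds residence, health-centre, income or employment data cannot be told from the documents.

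**What to change.** 1. Name in SAP 1.13 or 1.11 the variable that stands for each matching factor.
2. Add nationality and the already extracted baseline-year all-cause hospitalizations to the propensity score, using only the baseline part of the hospitalization count.
3. Add to the extraction list the number of outpatient and primary-care visits in the 365 days before index and, if I-Seha holds it, area of residence or registered health centre. Use both in the score.
4. Delete household income and employment status from the list unless I-Seha holds them.
5. Name the factors that remain unmeasured as confounders in Protocol 9.9. Show any illustrative bias in both directions.

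Cost: step 2 uses data already planned. The visit count is modest extra abstraction, since Protocol Annex 3 already requires outpatient visits in the 12-month baseline to be reviewed to identify immunocompromised patients. Residence or health centre would be an extra field per chart. More covariates may lose some matches among roughly 3000 treated patients and 1000 refusers; the documents do not allow that loss to be estimated. The rest is wording.

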### **1.13.1 Safety Analyses**

*Not applicable.*

### **1.13.2 Analyses of Endpoints**

*Not applicable.*

### **7.2.3 Summary of Analyses**

Descriptive statistics will be presented for all variables. Inferential statistics will be used to examine difference in demographic, clinical, and outcome characteristics between COVID-19 patients who received Paxlovid and those who were offered, but refused, Paxlovid.

PFIZER CONFIDENTIAL

CT24-WI-GL03-RF03 2.0 *Non-Interventional Statistical Analysis Plan For Secondary Data Collection*  
*Study 01-Jun-2020*  
Page 15 of 22

**LIST OF TABLES AND TABLE SHELLS****Table 3: Descriptive statistics for baseline variables**

Variables	Group		P-value	Effect size
	Paxlovid	Control		
Age, % (n)				
18-29				
30-49				
50-64				
65-74				
≥75 years				
Gender, % (n)				
Male				
Female				
Nationality, % (n)				
Bahrain				
Other Middle East and North Africa				
India				
Pakistan				
South East Asia				
Caucasian				

PFIZER CONFIDENTIAL

CT24-WI-GL03-RF03 2.0 *Non-Interventional Statistical Analysis Plan For Secondary Data Collection Study* 01-Jun-2020  
 Page 16 of 22

Enrollment Date Place of Service (POS), % (n)				
Office visit				
Emergency room				
Outpatient hospital				
Other				
Specialty of Provider at enrollment Date				
Interns				
Residents				
Family Phyiscans				
Specialist				
Consultants				
Number of days from COVID-19 symptom onset to resolution, mean (SD)				
Number of days from vaccination to contracting COVID-19, mean (SD)				
Number of days from contracting COVID-19 to being prescribed Paxlovid, mean (SD)				
Number of days from COVID-19 test to Paxlovid treatment, mean (SD)				
COVID-19 Lab Tests with Positive Result, % (n)				
COVID-19 Lab Test with Variant Type, % (n)				

PFIZER CONFIDENTIAL

CT24-WI-GL03-RF03 2.0 *Non-Interventional Statistical Analysis Plan For Secondary Data Collection Study* 01-Jun-2020  
 Page 17 of 22

**Table 6: Descriptive statistics for clinical characteristics**

Variables	Group		P-value	Effect size
	Paxlovid	Control		
Patient-reported Covid-19 symptoms, % (n)				
Stuffy or runny nose				
Sore throat				
Shortness of Breath				
Cough				
Low energy/Tiredness/fatigue				
Muscle ache/body aches				
Headache				
Chills or shivering				
Feeling hot/feverish				
Nausea or vomiting				
Diarrhea				
Loss of sense of smell				
Loss of sense of taste				
Comorbidities (ICD-10)				
Vaccination Status, % (n)				
Completely				

PFIZER CONFIDENTIAL

CT24-WI-GL03-RF03 2.0 *Non-Interventional Statistical Analysis Plan For Secondary Data Collection Study* 01-Jun-2020  
 Page 18 of 22

Partially				
Unvaccinated				
Risk factors for severe Covid-19, % (n)				
Age $\geq$ 50 years				
Obesity (BMI $\geq$ 35)				
Chronic kidney disease (eGFR $\geq$ 30 ml/min)				
Diabetes Mellitus				
Primary and Secondary Immunosuppressive disease or immunosuppressive treatment				
Cardiovascular disease (including congenital heart disease) or hypertension				
Chronic lung diseases (for example, chronic obstructive pulmonary disease, asthma [moderate-to-severe], interstitial lung disease, cystic fibrosis, and pulmonary hypertension)				
Sickle cell disease				
Neurodevelopmental disorders				
Having a medical-related technological dependence (for example, tracheostomy, gastrostomy, or positive pressure ventilation [not related to COVID-19])				
Death, % (n)				
Inpatient death, % (n)				

PFIZER CONFIDENTIAL

CT24-WI-GL03-RF03 2.0 *Non-Interventional Statistical Analysis Plan For Secondary Data Collection Study* 01-Jun-2020  
 Page 19 of 22

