### 9.2.2. Exclusion Criteria

**There are no exclusion criteria for this study.**

## 9.3 Variables

The following variables are used to obtain comprehensive descriptive results.

1. Demographics
2. Date of symptoms
3. Viral variant analysis where available (type of viral variant ie, omicron, delta etc.)
4. PCR date along with CT Value

5. Co-morbidities and
6. BMI if  $\geq 30$
7. Symptoms at presentation
8. COVID 19 vaccine status (NB 92% of population has been vaccinated -with at least one dose of COVID 19 vaccine- in Bahrain)
9. Hospital admission
10. Follow up looking at compliance and reason of non-compliance
11. Day 5,7, 21 and 28 symptoms for COVID-19 patients who receive and HRU limited to admission (ICU, ward, need for oxygen therapy) or death
12. Date of symptoms resolution if applicable

**Table 2** Table 2 below depicts the patient demographics that will be accessed during the baseline and follow-up periods. The baseline period is defined as one year before the index date. Comorbidities (full list in [Table 6](#)) and maintenance medication usage for chronic conditions (eg, statins, antihypertensives, etc.) will be described during the baseline period and follow-up periods and are listed in [Table 3](#).

Risk factors for severe COVID-19, intensive care unit (ICU) usage, invasive mechanical ventilation (IMV) usage, supplemental oxygen use, non-invasive ventilation, and high-flow nasal cannula usage are depicted in [Table 5](#) and will be extracted from the *I-Seha* national electronic health record database.

Where applicable, emerging treatment patterns may be assessed as the time from symptom onset to COVID-19 diagnosis, time from symptom onset to treatment initiation, and the time from COVID-19 diagnosis to treatment initiation as illustrated in [Table 5](#).

10Nov23 WHO recommendations for Paxlovid treatments to define: 1. COVID-19 patients who meet the WHO criteria for “strongly recommended” 2. COVID-19 patients who meet the WHO criteria for “conditionally recommended”, and 3. COVID patients who are not falling into categories 1 or 2 will be used.

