## 1.2 STUDY OBJECTIVES

The overall aim of this study is to examine the baseline demographic, clinical, and outcome characteristics of COVID-19 patients who received Paxlovid.

PFIZER CONFIDENTIAL

CT24-WI-GL03-RF03 2.0 *Non-Interventional Statistical Analysis Plan For Secondary Data Collection*  
*Study 01-Jun-2020*  
Page 6 of 22

The objectives are

- (i) to describe the demographic, clinical, and outcome characteristics of COVID-19 patients who received Paxlovid and COVID-19 patients who were offered, but refused Paxlovid
- (ii) to examine differences in the demographic characteristics (e.g., age, sex, nationality, type of outpatient encounter, vaccination status) between COVID-19 patients who received Paxlovid and COVID-19 patients who refused Paxlovid,
- (iii) to examine differences in the clinical characteristics (e.g., comorbidities, symptoms, duration of symptoms) between COVID-19 patients who received Paxlovid and COVID-19 patients who refused Paxlovid over a five-day follow-up,
- (iv) to examine differences in outcomes (e.g., hospitalisations, time spent in an intensive care unit, time spent with invasive mechanical ventilation, supplemental oxygen usage, re-admission to hospital, deaths) between COVID-19 patients who received Paxlovid and COVID-19 patients who refused Paxlovid over a five-day follow-up.
- (v) To examine differences in the proportion of COVID-19 patients who meet the most up-to-date WHO recommendations for the use of therapeutics in the treatment of COVID-19 (ie, version 14, published 10Nov2023) in comparison to Kingdom of Bahrain national recommendations.

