**Table 2: Clinical Characteristic Variables**

Variable	Operational definition
Comorbidities	Asthma, emphysema, chronic obstructive pulmonary disease (COPD), hypertension, diabetes, obesity, cerebrovascular disease, neurological disease, chronic kidney disease, chronic liver disease, malignancy, etc.
Risk Factors for Severe COVID-19	
 
• Age <math>\geq 50</math> years
 
• Obesity (BMI <math>\geq 35</math>)
 
• Chronic kidney disease (eGFR <math>\geq 30</math> ml/min)
 
• Diabetes Mellitus
 
• Primary and Secondary Immunosuppressive disease or immunosuppressive treatment
 
• Cardiovascular disease (including congenital heart disease) or hypertension
 
• Chronic lung diseases (for example, chronic obstructive pulmonary disease, asthma [moderate-to-severe], interstitial lung disease, cystic fibrosis, and pulmonary hypertension)
 
• Sickle cell disease
 
• Neurodevelopmental disorders (for example, cerebral palsy) or other conditions that confer medical complexity (for example, genetic or metabolic syndromes and severe congenital anomalies)
 
• Having a medical-related technological dependence (for example, tracheostomy, gastrostomy, or positive pressure ventilation [not related to COVID-19])
 

PFIZER CONFIDENTIAL

CT24-WI-GL03-RF03 2.0 *Non-Interventional Statistical Analysis Plan For Secondary Data Collection*  
 Study 01-Jun-2020  
 Page 9 of 22

Patient-reported COVID-19 symptoms	List of COVID-19 symptoms to be added by study team (US, CDC definition). 
 
1- Stuffy or runny nose
 
2- Sore throat
 
3- Shortness of Breath
 
4- Cough
 
5- Low energy/Tiredness/fatigue
 
6- Muscle ache/body aches
 
7- Headache
 
8- Chills or shivering
 
9- Feeling hot/feverish
 
10- Nausea or vomiting
 
11- Diarrhea
 
12- Loss of sense of smell
 
13- Loss of sense of taste
 

Death	Died on or after the enrollment date in the follow up period
Inpatient Death	Died during a hospitalization in the follow-up period

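### The 13 symptom rows in SAP Tables 2 and 6 have no time point, the documents imply conflicting ones, and the five-day comparison in objective (iii) rests on unequal symptom sources

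*SAP*

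**What the plan says.** **Protocol.** Section 9.3 lists two separate symptom variables. Item 7 is "Symptoms at presentation". Item 11 begins "Day 5,7, 21 and 28 symptoms for COVID-19 patients who receive"; the phrase is incomplete but appears to mean treated patients. Protocol Table 2, whose title ties its variables to the index date, holds the list of 13 symptoms. The sample results table (Table 8) puts the symptom, with its date, under baseline variables. Section 9.4.1 describes a telephone call about symptoms after Paxlovid initiation. For patients who did not take Paxlovid, it names chart extraction on re-evaluation in a facility, admission or death.

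**SAP.** Table 2 defines "Patient-reported COVID-19 symptoms" only as the same list of 13, with no date or window. Under Data source, the SAP says: "Patient-reported symptom outcomes in the five-days following Paxlovid prescription were determined by a follow-up telephone call". Objective (iii) is "to examine differences in the clinical characteristics (e.g., comorbidities, symptoms, duration of symptoms)" between recipients and refusers, over five days of follow-up. Table 6 gives the block "Patient-reported Covid-19 symptoms, % (n)" one row per symptom, with columns for both groups, a p-value and an effect size. No shell has day-specific symptom rows.

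**The concern.** A symptom percentage has no meaning without the day on which the question was asked, because acute symptoms change over days. The protocol keeps presentation and later days apart. The SAP merges them into one undated variable and tests it between groups.

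Two things are at stake. First, the protocol's primary objective is to describe baseline demographic and clinical characteristics in both groups, and presenting symptoms are part of that description, yet no SAP table is assigned to them. Second, objective (iii) read literally asks for a five-day comparison. Treated patients were telephoned and asked; for refusers the documents describe only records that arise if the patient returns, is admitted or dies. A difference between columns could then reflect how symptoms were ascertained.

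The point concerns the 13 symptom-prevalence rows, not symptom duration or time to resolution.

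**Working it through.** **1. Which time point applies?** The documents state no figure for symptoms, so there is nothing to reproduce. The check is a comparison of texts.

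| Place | Time point implied |
|---|---|
| Protocol 9.3, item 7 | Presentation |
| Protocol 9.3, item 11 | Days 5, 7, 21 and 28 |
| Protocol Table 2 | Index |
| Protocol Table 8, row 2.4 | Baseline, with date |
| SAP objective (iii) | Five-day follow-up |
| SAP Table 2 | None |
| SAP Table 6 | None |

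Elsewhere the SAP does fix timing: age is set at the diagnosis date, and most outcome variables name the baseline period, the follow-up period or both.

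**2. Can objective (iii) be met with like data in both groups?** Treated patients: the call, covering five days after prescription. Refusers: chart data on re-evaluation, admission or death, with no call described. Suppose a share r of refusers is re-evaluated and a share s of those has a given symptom. The control row shows s if the denominator is those assessed, or r × s if it is all refusers. The first may run high, since returning patients may be sicker; the second runs low. The direction therefore depends on a rule that the SAP does not give.

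**3. How sensitive would the tests be to a pure timing difference?** This is an illustration only. It supposes that one column held presenting symptoms and the other call symptoms, which the text allows but does not direct.

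Inputs from the SAP: about 3000 treated and 1000 refusers (Study population); alpha 0.05 per test with no multiplicity adjustment (Inferential statistics). Two-sided testing is assumed. Also assumed: presenting prevalence p is the same in both groups, and the call rate is q = p(1 − f), where f is the relative fall.

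Chance of p < 0.05 = Φ[(|p − q| − 1.96·SE0) / SE1], where SE0 uses the pooled rate and SE1 the separate rates.

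Worked case, p = 0.40 and f = 0.10:
- q = 0.36; pooled rate = (1000 × 0.40 + 3000 × 0.36)/4000 = 0.37
- SE0 = √[0.37 × 0.63 × (1/1000 + 1/3000)] = 0.01763
- SE1 = √[0.40 × 0.60/1000 + 0.36 × 0.64/3000] = 0.01780
- Φ[(0.04 − 0.03455)/0.01780] = Φ(0.306) = 0.62

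| Presenting rate | f = 5% | f = 10% | f = 25% |
|---|---|---|---|
| 20% | 10.5% | 29.5% | 95.1% |
| 40% | 20.3% | 62.0% | >99% |
| 60% | 38.3% | 91.3% | >99% |

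If only a quarter of treated records came from the call, with rates halved there and p = 0.40, then q = 0.40 × (1 − 0.5 × 0.25) = 0.35 and the chance is 81%. With no timing difference it is 5% per row.

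At f = 25% the differences are 5, 10 and 15 percentage points and Cramér's V is 0.059, 0.092 and 0.130. These lie near or below the SAP's benchmark for a weak association (0.1), even though the p-value would almost always be below 0.05.

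**The case against.** The strongest reply is that this is a missing label. The SAP's symptom entry repeats the protocol's list, which sits in an index table. The SAP says that EHR variables aligned with the protocol will be used. Its Data source section says that clinical data on eligible patients were recorded in the EHR, and the sentence about the call speaks of outcomes after prescription. Protocol section 9.4.1 also mentions a review of a symptom database without limiting it to treated patients. On that reading, both columns hold index symptoms from the chart.

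Much of this stands. A programmer could produce presenting symptoms for both groups, and the protocol still requires them. It does not settle the matter, because aligning with the protocol does not say which of its two symptom variables fills the row, and objective (iii) points to follow-up. The symptom database is given no time window, so it does not supply a five-day source for refusers.

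Two stronger readings are tempting and should not be adopted:

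- A reader might infer that Table 6 presents post-treatment symptoms as a baseline characteristic. Its title is "Descriptive statistics for clinical characteristics", it also holds death rows, and the SAP table headed "Descriptive statistics for baseline variables" is a different one with no symptom-prevalence rows. The baseline label comes from the protocol.
- A reader might infer that the plan puts call symptoms in the treated column and presenting symptoms in the control column. No text directs this. The SAP names no separate symptom source for refusers, so what their column would hold is inference.

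It is also fair that the SAP has no hypotheses or decision rules and calls the work exploratory, which limits the consequences.

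**Conclusion.** The point holds in this form: the symptom time point is undefined in SAP Tables 2 and 6, and the time points implied elsewhere conflict (index or presentation in the protocol, five-day follow-up in SAP objective (iii)). It is more than a label, because the five-day comparison has a described source for treated patients only, and presenting symptoms have no assigned shell.

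All 13 rows are affected. The size and direction of any distortion are unknown. The probabilities above rest on assumed rates and on a mixing of sources that the plan permits but does not prescribe. They show only that, at these group sizes, modest timing differences could yield significant rows with no real difference between groups. If treated patients were instead counted as ever having the symptom at presentation or on the call, the distortion would run the other way.

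This should be corrected before analysis. It does not undermine the rest of the descriptive plan.

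**What to change.** - In SAP Tables 2 and 6, define the symptom rows as symptoms at presentation, on or before the index date, from the same source and window in both groups. Limit the between-group p-value and effect size to these rows.
- Add a separate descriptive shell for post-index symptoms: day 5, and days 7, 21 and 28 where available. Give the number assessed and the source for each. Restrict it to treated patients unless equivalent refuser data exist.
- Amend objective (iii) so that the symptom comparison refers to presentation and later symptoms are described only.

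The cost is SAP wording and one extra shell. The between-group five-day symptom test is given up, but the data described do not support it. The day 7, 21 and 28 rows may prove hard to fill, since the SAP ties the call to five days and extracts variables only if available; reporting the number assessed makes that visible.
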